7.4.2.2 Infusion Interruptions and Rate Changes

The following parameters will be summarized:

- Number of subjects with at least one dose infusion interruption, number of infusion interruptions per subject and the reason for interruption.

- Number of subjects with at least one IV infusion rate reduction, number of IV infusion rate reduction per subject and the reason for reduction

7.4.2.3 Dose Reductions/Escalation

There will be no dose escalations or reductions of nivolumab allowed.

7.4.3 Concomitant Medications

Concomitant medications, defined as medications other than study medications which are taken at any time on-treatment (i.e. on or after the first day of study therapy and within 100 days following the last dose of study therapy), will be coded using the WHO Drug Dictionary.

The following summary tables will be provided:

- Concomitant medications (subjects with any concomitant medication, subjects by medication class and generic term).

A by-subject listing will accompany the table.

7.5 Efficacy

7.5.1 Primary endpoint of ORR (IRRC-assessed)

The IRRC-assessed ORR (using revised IWG Criteria for Malignant Lymphoma criteria) will be summarized on the all subjects treated population by a binomial response rate. The Clopper-Pearson³⁷ method will be used to estimate the two-sided 95% CI.

BOR will be summarized by response category.

Summary statistics of time to objective response will be provided for subjects who achieve PR or CR, as assessed by the IRRC. CR requires confirmation by PET. To assess tumor response kinetics, time to response will also be analyzed using the KM methodology for all treated subjects. Kaplan-Meier curve will represent the cumulative rate of response over time. For the non-responders, time to response will be censored at the maximum time of response + 1 day of all subjects. Cumulative Response Rates will be tabulated for Week 9, Month 4, 6, 8, 12 and 18, and overall Response Rate will be provided.

7.5.1.1 ORR Subgroups

To assess consistency of ORR, IRRC-assessed ORR (primary analysis) will be summarized for the following subgroups:

- Age (< 65, ≥ 65 and < 75, ≥ 75)
- Region (US/Canada, Europe, Rest of the world).
- Gender (Male, Female)
- Race (White, Black or African American, Asian, and Other (pooling all other possibilities))
- Smoking status (current/former vs never smoker vs unknown)

- ECOG (0, 1, >1, NOT REPORTED)
- Number of prior therapies (0, 1, 2, 3, 4, ≥ 5)
- Prior Autologous Transplant (Yes, No)
- Time from most recent prior systemic cancer therapy to first dose of nivolumab (< 3 months, 3 - 6 months, > 6 months)
- Refractory, Relapsed Lymphoma (which is the disease diagnosis status at study entry)
- FLIPI Score (0-1, 2, 3, 4-5)

Categories including less than 5 subjects may be collapsed. Analyses of subgroups of less than 5 subjects may not be provided.

7.5.1.2 Sensitivity analyses for ORR

- As sensitivity analysis, a summary of IRRC-assessed ORR based on response evaluable subjects instead of all treated subjects will also be presented. Clopper Pearson 95% CI will be used in this analysis.
- To assess concordance between IRRC (primary analysis) and investigator assessments, BOR will be cross-tabulated by assessment type (Investigator vs IRRC). Concordance Rate of Responders will be computed as the frequency with which Investigator and IRRC agree on classification of a subject as responder/non responder as a proportion of the total number of subjects assessed.

7.5.2 Secondary Endpoint of Duration of Response (IRRC-assessed)

The DOR will be summarized for subjects who achieve PR or CR as determined by IRRC using KM product-limit method. Two-sided, 95% confidence intervals for median DOR will be constructed based on log-log transformation. Range of duration of response and the number of ongoing responders will also be presented. In addition, the percentage of responders still in response at different time points (3, 6 and 12 months) will be presented based on the DOR KM plot.

The status of subjects who are censored in the duration of response analysis will be tabulated using the following categories:

- received subsequent anti-cancer therapy
- off-study (with reason)

Duration of stable disease will also be estimated using KM product-limit method for subjects with SD as best response. Two-sided, 95% confidence intervals for median duration of SD will be computed.

7.5.3 Secondary Endpoint of Complete Remission Rate (IRRC-assessed)

IRRC-assessed CRR will be summarized by a binomial response rate and its corresponding two-sided 95% exact CIs using the Clopper-Pearson³⁷ method.

To further characterize CRR, the duration of CR will be summarized for subjects who achieve CR as determined by IRRC using KM product-limit method. Two-sided, 95% confidence intervals for median duration of CR will be constructed based on log-log transformation. Range of duration of CR will also be presented.

7.5.4 Secondary Endpoint of Partial Remission Rate and Duration (IRRC-assessed)

IRRC-assessed PRR will be summarized by a binomial response rate and its corresponding two-sided 95% exact CIs using the Clopper-Pearson³¹ method.

To further characterize PRR, the duration of PR will be summarized for subjects who achieve PR as determined by IRRC using KM product-limit method. Two-sided, 95% confidence intervals for median duration of PR will be constructed based on log-log transformation. Range of duration of PR will also be presented.

7.5.5 Secondary Endpoint of Progression Free Survival (IRRC-assessed)

IRRC-assessed PFS will be summarized descriptively using the Kaplan-Meier (KM) product-limit method. Median values of PFS, along with two-sided 95% CIs (based on the log-log transformation), will also be calculated.

The source of progression (death vs. progression) will be summarized.

The status of subjects who are censored in the PFS Kaplan-Meier analysis will be tabulated using following categories:

- Received subsequent anti-cancer therapy (Stem Cell Transplant, other)
- Still on-treatment
- Progression-free in follow-up
- Off-study: (lost to follow-up, withdrew consent, other).

KM curve of PFS will be generated. PFS rates per IRRC at 6, 9 and 12 months will be estimated using KM estimates on the PFS curve. PFS rates at 18, 24 and 36 months may also be estimated depending on whether minimum follow-up will be longer than timepoint to generate the rate. Associated two-sided 95% CIs will be calculated.

KM curves of PFS by response of most recent prior systemic cancer therapy as well as KM curves of PFS by number of prior systemic anti-cancer therapy lines will also be generated. Some categories may be collapsed to have sufficient number of subjects in each category. Median values of PFS in each category along with two-sided 95% CIs (based on the log-long transformation) will also be calculated.

7.5.6 Secondary Endpoint of Objective Response Rate (Investigator-assessed)

Investigator-assessed ORR will be summarized by a binomial response rate and its corresponding two-sided 95% exact CIs using the Clopper-Pearson³⁷ method:

Investigator-assessed BOR will be summarized by response category.

Summary statistics of time to objective response will be provided for subjects who achieve PR or CR, as assessed by the Investigator. CR requires confirmation by PET. To assess tumor response kinetics, time to response will also be analyzed using the KM methodology for all treated subjects. Kaplan-Meier curve will represent the cumulative rate of response over time. For the non-responders, time to response will be censored at the maximum time of response + 1 day of all subjects. Cumulative Response Rates will be tabulated for Week 9, Month 4, 6, 8, 12 and 18, and overall Response Rate will be provided.

7.5.7 Exploratory Endpoints

[REDACTED]

[REDACTED]

[REDACTED]

[REDACTED]

[REDACTED]

[REDACTED]

[REDACTED]

[REDACTED]

[REDACTED]

[REDACTED]

[REDACTED]

[REDACTED]

[REDACTED]

[REDACTED]

[REDACTED]

[REDACTED]

[REDACTED]

[REDACTED]

[REDACTED]

[REDACTED]

[REDACTED]

[REDACTED]

[REDACTED]

[REDACTED]

[REDACTED]

[REDACTED]

[REDACTED]

[REDACTED]

[REDACTED]

7.6 Safety

All analyses from the Core Safety SAP²⁹ will be produced.

7.6.1 Deaths

See Core Safety SAP²⁹.

7.6.2 Serious Adverse Events

See Core Safety SAP²⁹.

7.6.3 Adverse Events Leading to Discontinuation of Study Therapy

See Core Safety SAP²⁹.

7.6.4 Adverse Events Leading to Dose Modification

See Core Safety SAP²⁹.

7.6.5 Adverse Events

See Core Safety SAP²⁹.

7.6.6 Select Adverse Events

See Core Safety SAP²⁹.

7.6.7 Immune modulating medication

See Core Safety SAP²⁹.

7.6.8 Multiple Events

See Core Safety SAP²⁹.

7.6.9 Clinical laboratory evaluations

See Core Safety SAP²⁹.

7.6.10 Vital Signs and Pulse Oximetry

See Core Safety SAP²⁹.

7.6.11 Immunogenicity Analysis

See Core Safety SAP²⁹.

7.6.12 Pregnancy

By-subject listing of pregnancy tests results will be provided

7.6.13 Clinical Safety Program (CSP)

See Core Safety SAP²⁹.

7.6.14 Adverse Events by Subgroup

See Core Safety SAP²⁹.

7.6.15 Immune-mediated Adverse Events Analysis

See Core Safety SAP²⁹.

7.7 Pharmacokinetics

The nivolumab concentration data obtained in this study may be combined with data from other studies in the clinical development program to develop or refine a population PK model. This model may be used to evaluate the effects of intrinsic and extrinsic covariates on the PK of nivolumab and to determine measures of individual exposure (such as steady-state peak, trough, and time-averaged concentration). In addition, model determined exposures may be used for exposure-response analyses. Results of population PK and exposure response-analyses will be reported separately.

7.8 Biomarker Analyses

[REDACTED]

[REDACTED]

[REDACTED]

[REDACTED]

[REDACTED]

[REDACTED]

[REDACTED]

[REDACTED]

[REDACTED]

[REDACTED]

[REDACTED]

[REDACTED]

[REDACTED]

[REDACTED]

7.9 Outcome Research Analyses

7.9.1 EORTC-QLQ-C30 Questionnaire

Unless otherwise specified, the analysis of EORTC QLQ C-30 will be performed in all treated subjects who have an assessment at baseline and at least one subsequent assessment. Analyses will be performed.

Baseline measures will be summarized using descriptive statistics (N, mean, standard deviation, median, first and third quartiles, minimum, maximum) for each QLQ-C30 item, as well as global and functional scales, based on subjects with a baseline measurement.

Change from baseline will be summarized using descriptive statistics (N, mean, standard deviation, median, first and third quartiles, minimum, maximum) for each QLQ-C30 item, as well as global and functional scales at each assessment time point. In addition, the percentage of subjects demonstrating a clinically meaningful deterioration (defined as a 10 point change from baseline) will be presented for each scale at each assessment timepoint. Percentages will be based on number subjects assessed at baseline and at assessment time point.

EORTC-QLQ-C30 questionnaire completion rate, defined as the proportion of questionnaires actually received out of the expected number (i.e., number of subjects on treatment or in follow up), will be calculated and summarized for each assessment time point.

A by subject listing of QLQ-C30 with each QLQ-C30 item, functional scales and global health status will be provided.

7.9.2 EQ-5D Questionnaire

Unless otherwise specified, the analysis of EQ-5D will be performed in all treated subjects who have an assessment at baseline and at least one subsequent assessment. Analyses will be performed.

Subject's overall health state on a visual analog scale (EQ-VAS) at each assessment time point will be summarized using descriptive statistics (N, mean, SD, median, 25th and 75th percentiles, minimum, maximum).

Proportion of subjects reporting problems for the 5 EQ-5D dimensions at each assessment time point will be summarized by level of problem. Percentages will be based on number subjects assessed at assessment time point.

A by-subject listing of EQ-5D with the problem levels for each of the 5 dimensions (mobility, self-care, usual activities, pain/discomfort and anxiety/depression), health state (5 dimensions digits combined in a 5-digit number) and EQ-VAS will be provided.

Results of EQ5D-Index will be presented separately and will be described in the GHEOR SAP.

7.10 Interim Analysis

No interim analysis planned. Interim analyses may be conducted if it is necessary in order to make decisions regarding further development. Summaries and listings of efficacy and safety will be provided. Interim analyses will not impact the study duration and the trial will continue as planned.

8 CONVENTIONS

The following conventions may be used for imputing partial dates for analyses requiring dates:

For missing and partial adverse event onset dates, imputation will be performed using the Adverse Event Domain Requirements Specification³⁸. Missing and partial Non-Study Medication Domain dates will be imputed using the derivation algorithm described in BMS Non-Study Medication Domain Requirements Specification³⁹.

For death dates, the following conventions will be used for imputing partial dates:

- If only the day of the month is missing, the 1st of the month will be used to replace the missing day. The imputed date will be compared to the last known alive date and the maximum will be considered as the death date.
- If the month or the year is missing, the death date will be imputed as the last known alive date
- If the date is completely missing but the reason for death is present the death date will be imputed as the last known alive date

For date of progression, the following conventions will be used for imputing partial dates:

- If only the day of the month is missing, the 1st of the month will be used to replace the missing day.
- If the day and month are missing or a date is completely missing, it will be considered as missing.

- In case, the date of death is present and complete, the imputed progression date will be compared to the date of death. The minimum of the imputed progression date and date of death will be considered as the date of progression.

For other partial/missing dates, the following conventions will be used:

- If only the day of the month is missing, the 15th of the month will be used to replace the missing day.
- If both the day and the month are missing, “July 1” will be used to replace the missing information.
- If a date is completely missing, it will be considered as missing.

The following conversion factors will be used to convert days to months or years: 1 month = 30.4375 days and 1 year = 365.25 days.

Duration (e.g. time from first diagnosis to first dosing date, duration response, and time to response) will be calculated as follows:

$$\text{Duration} = (\text{Last date} - \text{first date} + 1)$$

All statistical analyses will be carried out using SAS (Statistical Analysis System software, SAS Institute, North Carolina, USA) unless otherwise noted.

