#### **3.6.1 Withdrawal of Consent**

Subjects who request to discontinue study treatment will remain in the study and must continue to be followed for protocol specified follow-up procedures. The only exception to this is when a subject specifically withdraws consent for any further contact with him/her or persons previously authorized by subject to provide this information. Subjects should notify the investigator of the decision to withdraw consent from future follow-up **in writing**, whenever possible. The withdrawal of consent should be explained in detail in the medical records by the investigator, as to whether the withdrawal is from further treatment with study drug only or also from study procedures and/or post treatment study follow-up, and entered on the appropriate CRF page. In the event that vital status (whether the subject is alive or dead) is being measured, publicly available information should be used to determine vital status only as appropriately directed in accordance with local law.

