4.2.4 Progression Free Survival (IRRC-assessed)

Progression free survival (PFS) is defined as the time from first dosing date to the date of the first documented progression, as determined by an IRRC according to the 2007 revised International Working Group Criteria for Malignant Lymphoma, or death due to any cause, whichever occurs first.

- Subjects who have no baseline tumor assessment will be censored at their first dosing date.

- Subjects who have baseline tumor assessment and who die without a reported progression will be considered to have progressed on the date of their death.
- Subjects who did not progress or die will be considered as not progressed and will be censored on the date of their last assessment.
- Subjects who did not have any on study assessments and did not die will be censored on the first dosing date.
- Subjects who started any subsequent anti-cancer therapy without a prior reported progression will be censored at the last assessment prior to or on their first subsequent therapy date.

Table 4.2.4-1: Censoring scheme used in primary analysis of PFS

Situation	Date of Progression or Censoring	Outcome
No baseline tumor assessments	First Dosing date	Not Progressed
No on study tumor assessments and no death	First Dosing date	Not Progressed
No progression per 2007 IWG criteria and no new anti-cancer treatment started	Date of last tumor assessment with no documented progression per the 2007 IWG criteria	Not Progressed
New anticancer treatment started without a prior reported progression per 2007 IWG criteria	Date of last tumor assessment prior or on the date of initiation of the subsequent anti-cancer therapy	Not Progressed
Progression per 2007 IWG criteria documented between scheduled visits or at scheduled visit without prior new anticancer treatment started	Date of the first documented tumor progression per the 2007 IWG criteria	Progressed
Death without progression per 2007 IWG criteria and without prior new anticancer treatment started	Date of death	Progressed

To further characterize PFS, progression by response to most recent prior systemic cancer therapy and progression by number of prior systemic cancer therapy lines may also be evaluated.

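### For a death with a known year but no month, SAP section 8 uses the last known alive date and ignores the year, so the death can fall in a year the record excludes

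*SAP*

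**What the plan says.** SAP section 8 gives three rules for incomplete death dates.

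1. Day missing: "If only the day of the month is missing, the 1st of the month will be used to replace the missing day", and then "The imputed date will be compared to the last known alive date and the maximum will be considered as the death date".
2. Month or year missing: "If the month or the year is missing, the death date will be imputed as the last known alive date".
3. Whole date missing: "If the date is completely missing but the reason for death is present the death date will be imputed as the last known alive date".

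The same section keeps a known year for dates other than death and progression: "If both the day and the month are missing, “July 1” will be used to replace the missing information". A progression date without day and month is treated as missing.

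The death date is an event date in several endpoints. SAP Table 4.2.4-1 counts as a PFS event, on the date of death, the case "Death without progression per 2007 IWG criteria and without prior new anticancer treatment started". SAP 4.2.1 to 4.2.3 count death from any cause as an event in DOR and in the durations of SD, CR and PR. The SAP's schedule of analyses also plans survival analysis for up to 5 years beyond the primary analysis.

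On follow-up, Protocol 3.1 plans survival contact every 3 months after the two safety visits. Protocol 3.6.2 asks sites to obtain the date and cause of death when a subject lost to follow-up is found to have died. Protocol 3.6.1 says that, where vital status is measured after withdrawal of consent, "publicly available information should be used to determine vital status only as appropriately directed in accordance with local law".

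**The concern.** The second rule covers two different situations. When the year is missing, the last known alive date is about all that is left. When the year is known and only the month is missing, the record still sets a lower limit of 1 January of that year. The rule discards that limit and gives the same answer as the third rule, where nothing about the date is known. The first rule works differently: it takes the earliest date that agrees with both the partial date and the last known alive date.

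At stake is a death event placed on a date that the trial's own record contradicts. The error has one direction: the imputed date can be too early but never too late. It would enter the Kaplan-Meier summaries of PFS, DOR, the duration endpoints and survival.

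**Working it through.** The plan states no figure on this point, so the check applies the rules to examples.

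**Inputs.** The three death-date rules and the conversion of 30.4375 days per month come from SAP section 8. The 3-month contact interval comes from Protocol 3.1. All calendar dates below are illustrative assumptions.

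**Step 1. Which rule applies.** A record of death in 2016 with no month does not meet the first rule, because more than the day is missing. It does not meet the third, because the date is not wholly missing. The second applies, and the imputed date is the last known alive date (LKA). No unredacted text in either document overrides this.

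**Step 2. When the result contradicts the record.** The earliest date the record allows is max(1 January of the known year, LKA). The SAP date is LKA. The difference is max(0, 1 January of the known year − LKA). It is positive only if LKA lies in an earlier calendar year.

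| LKA | Recorded death | SAP date | Earliest date the record allows | Shift |
|---|---|---|---|---|
| 20 Dec 2015 | 2016 | 20 Dec 2015 | 1 Jan 2016 | 12 days (0.4 months) |
| 15 Oct 2015 | 2016 | 15 Oct 2015 | 1 Jan 2016 | 78 days (2.6 months) |
| 10 Mar 2015 | 2016 | 10 Mar 2015 | 1 Jan 2016 | 297 days (9.8 months) |
| 1 Nov 2014 | 2016 | 1 Nov 2014 | 1 Jan 2016 | 426 days (14.0 months) |
| 10 Feb 2016 | 2016 | 10 Feb 2016 | 10 Feb 2016 | none |

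Each shift is a minimum for the true error, since the death may have come later in the year.

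**Step 3. Comparison with the day-missing rule.** Take LKA 15 October 2015 and death recorded as January 2016. The first rule gives max(1 January 2016, 15 October 2015) = 1 January 2016, which agrees with the record. If the month is removed from the same record, the date moves back to 15 October 2015, in the wrong year.

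**Step 4. How large and how often.** With unbroken contact, the gap from LKA to death is at most about 3 × 30.4375 = 91 days, so the error is at most about 3 months. Now assume that death is uniform over the year and that the gap is uniform from 0 to G days. For G up to one year, the share of year-only deaths placed in the wrong year is (G/2)/365.25:

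- G = 30: 15/365.25 = 4%
- G = 91: 45.5/365.25 = 12%
- G = 182: 91/365.25 = 25%
- G = 365: 182.5/365.25 = 50%

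A simulation under the same assumptions gave the same shares. The documents do not say how many deaths will lack a month. If it were 0 to 2 of 90 (an assumption), the expected number in the wrong year would be 0 to 2 × 0.12 = 0.24 subjects for gaps up to 91 days, and 0 to 2 × 0.50 = 1 for gaps up to a year. One subject is 1/90 = 1.1% of the treated population.

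**The case against.** **The conventions are optional.** Section 8 opens with "The following conventions may be used for imputing partial dates for analyses requiring dates". This carries little weight: the line that introduces the death-date rules is worded as binding, and no alternative rule is given.

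**Early dating is conservative, and later dating could flatter PFS and DOR.** Table 4.2.4-1 has no censoring for missed assessments. A later death date would therefore credit a subject who was out of contact with unassessed time as progression-free or in response. That is true, but it comes from the censoring scheme and applies equally to a fully known death date. The SAP dates a PFS death event on the date of death. The date proposed here is still the earliest the record allows, so it keeps the conservative direction without contradicting the record.

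**The effect on PFS and DOR is narrow.** Death is a PFS event only without prior progression or new anticancer treatment, and starting new therapy also censors DOR. This stands. The definition and methods for overall survival are redacted, so how death dates enter that analysis cannot be checked here.

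**Stronger readings do not hold.** A reader might infer that every year-only death is misplaced. It is not: when last contact was in the year of death, the imputed date agrees with the year on record. A reader might also infer that year-only dates come mainly from subjects traced through public records. Protocol 3.6.1 and 3.6.2 allow such tracing but do not suggest that it yields only a year. Nor is a very large shift typical. With LKA 15 March 2015 and death recorded as 2017, the shift is 658 days (658/30.4375 = 21.6 months), but that needs about 658/91 ≈ 7 missed 3-monthly contacts in a row.

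**Conclusion.** Wrong as written, and minor. The rule discards a known year of death. Whenever the last known alive date lies in an earlier calendar year, it dates the death in a year the record excludes, always too early. This follows from the wording of section 8 and needs no assumption about the data.

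The size does rest on assumptions. The shift is about 3 months at most if 3-monthly contact is kept, and longer only after a long loss of contact. The number of subjects affected is not given and may be zero. The effect is confined to descriptive secondary summaries (PFS, DOR, durations of CR and PR), the additional duration of SD, and survival. The primary IRRC-assessed ORR and its test against 20% are unaffected.

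**What to change.** Split the second death-date rule in SAP section 8:

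- If the year is known and the month is missing, impute the later of 1 January of the known year and the last known alive date.
- If the year is missing, impute the last known alive date, as now.

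This extends the SAP's day-missing rule to the month and changes nothing when last contact was in the year of death. It costs one sentence in the SAP and the matching change in the date-derivation program, with no new data collection.
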